7.1.6. Efficacy Evaluation Method

1) Description of efficacy parameters

The efficacy endpoints and their definitions are the following:

- Technical Success, defined as a combination of A0 ablations (complete tumor ablation with a surrounding 5 mm margin) and A1 ablations (complete tumor ablation with inadequate margins) based on contrast-enhanced MRI, performed up to 7 days following the original ablation procedure.
- Technical Efficacy, defined as a combination of A0 ablations (complete tumor ablation with a surrounding 5 mm margin) and A1 ablations (complete tumor ablation with inadequate margins), based on contrast-enhanced MRI scans at 1 month (+/- 7 days) after the original ablation procedure.
- Local tumor progression (LTP), evaluated at every visit after the ablation of the target tumor(s). LTP describes the appearance of tumor foci at the edge of the ablation zone, after at least one contrast-enhanced follow-up MRI scan has documented adequate ablation and an absence of viable tissue in the target tumor and surrounding ablation margin by using imaging criteria.
- Secondary efficacy rate, defined as the percentage of tumors that have undergone successful repeat ablation following identification of local tumor progression at any time during study follow up.
- Progression free survival, defined as length of time from the original ablation procedure until any type of disease progression (i.e. local or distant).
- Overall survival measured from the time of the original ablation procedure to the time
 of death or last follow-up if death has not occurred.

2) Selection of method and time to evaluate, record, and analyze the efficacy parameters

The primary effective parameters in this study will be assessed by the investigator(s) at each site based on examining image data.

7.1.7. Safety Evaluation Method

1) Description of safety parameters

The safety parameters in this study are all AEs and SAEs for 30 days after any ablation procedure (original or additional); after 30 days post an ablation procedure through the end of the study, only SAEs will be reported and assessed. The safety endpoint is the rate of AEs and SAEs reported at each analysis and cumulatively throughout the entire study period.

2) Selection of method and time to evaluate, record, and analyze the safety parameters

Confidential Page 31 of 61

NeuWave Medical, Inc. NEU_2017_07

06 AUGUST 2020, VERSION: 4.0

Patients will be assessed for all AEs and SAEs for 30 days after any ablation procedure (original or additional); after 30 days post an ablation procedure through the end of the study, only SAEs will be reported. The safety parameters are recorded on the e-CRF according to the investigator's record, medical record, and all other related source documents, which are collected at each follow-up visit.

7.2. Study Process

7.2.1. Study Flowchart

Refer to Table 1: Schedule of Activities, which may be found at the end of the Protocol Summary.

7.2.2. Procedure Description

[figure not shown]
Patients who have who have a single HCC tumor up to 5 cm or a maximum of 3 HCC tumors of up to 3 cm per tumor will receive the same procedure: microwave ablation using only the NeuWave Certus Microwave Ablation System. Patients in this study will come to their study site for the ablation procedure. After the ablation procedure, the patient will be observed, which in most cases is expected to be 2 to 3 hours, and afterwards may return home; If the Study Doctor decides it is warranted for patient safety, the patient will remain longer.

A minimum of one MRI of the liver must be taken at Baseline/Screening to ascertain tumor type, location, and size. (Tumor size will be measured in longest diameter and the diameter that is perpendicular to this longest diameter; tumor size must be measured with at least 2D imaging.) Physicians who are experienced with tumor ablation will do all ablations percutaneously using only the NeuWave Certus Ablation System. During the ablation, patients will be under an anesthesia method as per the institution's SOC. Ultrasound and/or CT scan will be used to guide the probe to the tumor and confirm accurate placement of the probe prior to emitting the microwaves.

Within 7 days after ablation, contrast-enhanced MRI will be done to confirm the completion of the ablation procedure. According to the standard practice at each study site, ablation confirmation will be classified as:

- Complete tumor ablation with adequate margin (A0).
- Complete tumor ablation with insufficient margin (A1).
- Incomplete tumor ablation (A2).

Confidential Page 32 of 61

Over the course of 3 years, patients will return to their study site for post ablation follow-up visits, which will be carried out per the Schedule of Activities (see Table 1 at the end of the Synopsis). At every follow-up visit, the patient will be scanned with at least one MRI to see if there are any tumor foci at the edge of the ablation zone, which indicates local tumor progression (LTP). These MRIs will also serve as the basis for determining progression-free survival, defined as length of time from the original ablation procedure until any type of disease progression (i.e. local or distant).

Microwave ablation (using the Certus Microwave Ablation System only) may be performed for recurrence of target tumor(s) or to achieve complete tumor ablation with adequate margin (A0) of the target tumor(s) if the initial ablation had an insufficient margin, if the treating physician deems appropriate and necessary. While repeat ablations for a recurrence may be conducted at any point during the study duration, repeat ablations to correct an ablative margin may only be performed within the first 30 days of the original ablation (by Visit 3).

7.2.3. Standard Operating Procedures of Medical Device

According to Instructions For Use (IFU) and technical manual of the product, the requirements for the use of study product are as follows:

a. Indications and scope of application:

The NeuWave Certus Microwave Ablation System is indicated for the ablation (coagulation) of soft tissue. The NeuWave Certus Microwave Ablation System is not indicated for use in cardiac procedures. The system is designed for facility use and should only be used under the orders of a physician

b. Recommended operating mode for the Certus system:

Physicians who are experienced with tumor ablation will do all ablations percutaneously Confidential Page 33 of 61

using only the NeuWave Certus Ablation System. During the ablation, patients will be under an anesthesia as per the institution's SOC. Microwave ablation is a minimally invasive procedure that uses electromagnetic waves to generate tissue necrosis in the liver in this study. Using contrast-enhanced ultrasound imaging or CT scan guidance, a small probe is inserted percutaneously into the tumor.

The ablation will be performed with a single high-powered, gas-cooled, multiple antenna—capable MW system (NeuWave Medical's Certus Ablation System and Accessories) with single or multi-probe antennas, according to the IFU and the performing physician's clinical judgment. Electromagnetic waves are delivered to the tissue, producing frictional heating to generate tissue necrosis at > 60°C. Duration of the ablation and power application will be determined by the performing physician based on manufacturer guidelines, with adjustment for tumor size, proximity to vulnerable structures, and real-time intraprocedural monitoring. Antenna placement may be performed under real-time contrast- enhanced ultrasound imaging guidance. Single or multiple ablation sessions may be done in one procedure. It is suggested that the physician considers using more than one probe for tumors ≥ 2 cm.

The Certus Ablation System rests on a cart that contains the MW power amplifiers and cooling system. The user interface for the Certus Ablation System is a system display to access all controls and settings. When ready to begin the procedure, the display will be used to select the tissue locations in which probes will be inserted during the procedure.

Target ablation involves placing a probe into a substantial target and then ablating for up to several minutes until the target tissue is necrotic. This is done either percutaneously, via laparoscope, or in open surgical settings. In Ablation Mode, power delivery times can be set from 1 to 10 minutes per delivery. The efficiency at which different types of soft tissue receive MW energy differ based on the electrical properties of the tissue. The design differences in certain Certus Ablation Probes are intended to optimize the efficiency of energy transferred from the probe into different tissue types. Model Certus LK probes are designed to optimize energy transfer efficiency in liver tissue based on tissue properties.

Ablation time and power will also be controlled via the system display, which has buttons to control for Time and Power. Pressing the buttons next to the Time box adds or subtracts from the Target Time in 1-minute increments. The buttons next to the Power box add or subtract from the Power in 5-Watt increments.

Each connected probe must successfully pass a functional test before Tissu-Loc™, Ablate, or Cauterize buttons are activated. The functional test must be conducted and passed before a probe may be used for ablation or surgical functions. Once a probe passes, the functional controls become active.

Pressing the Ablation Tissu-LocTM button starts the CO₂ cooling system to cool the Tissu-LocTM zone in the probe to between 0 and -15°C. Once the Tissu-LocTM Zone temperature reaches -5° C, the button turns gray, a green check mark appears on the button, and the button text reads 'Stop Tissu-LocTM.

Confidential Page 34 of 61

The Probe Temperature is displayed below the probe image. A green highlighted outline appears around the Time box to indicate that power is being delivered. The Time display begins to count down from the target Time or count up to the target Time. An audible tone sounds continuously to indicate that power is being delivered. If more than one probe is delivering power, the audible tone changes pitch.

When the Stop Ablate button or Stop All Ablation Bar is pressed, energy delivery is stopped, and the Ablation Time is displayed below the Time Box. This indicates the total time that power has been delivered via that probe. The probe temperature remains on the display.

A cauterizing feature is available to cauterize the insertion track when removing the probe from the patient. This feature is to cauterize the insertion track only. It should not be used to ablate or cauterize target tissue. Only one probe can be used in Cauterize mode at a time. No other probes may be delivering energy when cauterizing with a probe.

After the probe is removed from the patient, the Certus Ablation System cart may be wheeled to the side to allow the doctor to clean and bandage the probe insertion site.

c. Warnings and precautions

All hazards associated with the use of the Certus have been identified and appropriately mitigated. Design considerations were taken to reduce the risks associated with existing MW ablation systems, including improved system usability and cable management.

Important: Probe temperatures are highly dependent on tissue variables such as perfusion and vasculature. Probe temperatures are likely to vary from procedure to procedure based on these tissue variables. These temperature variations do not, by themselves, indicate a malfunctioning probe or system.

Electrosurgical/electrocautery devices may interfere with the Certus system and cause system errors. Ensure that all Certus probes are removed from the patient prior to using electrosurgical/electrocautery devices.

Use only Certus Ablation Probes from NeuWave Medical with the Certus Ablation System. Probes from other manufacturers may cause patient injury or fail to function properly.

The Certus system uses a CO₂ cooling system where all other MW systems use sterile water, but the risks associated with this cooling system do not differ from the risks inherent in cryogenic ablation systems, also widely accepted in clinical use. Thus, the Certus system does not introduce new hazards or intended uses.

This product should only be used by clinicians and staff properly trained in the use of the technology and its associated warnings and cautions.

Refer to the Certus Microwave Ablation System and Accessories accompanying documents for a complete and comprehensive list of Warnings and Cautions.

Confidential Page 35 of 61

7.2.4. Study Procedures

Screening

Patients will be consented prior to any actual study-specific screening procedures being conducted. Patients will be considered enrolled into the study upon satisfaction of the following criteria:

- Completion of the informed consent process and signing the Informed Consent Form (ICF).
- Verification of the eligibility criteria (Section 7.1) by the Principal Investigator (PI) and/or authorized investigators. The verification must be conducted by the PI and/or authorized investigators prior to performing any study-related procedure or completing any form associated with this study.

Screening Failures

Screened patients who are not enrolled will be considered screen failures. For patients who are determined to be screen failures, only the following data will be recorded on the eCRF:

- Informed consent date.
- Demographic information (age, race, gender, and ethnicity).
- Reason for screening failure.

Randomization

This is a single-arm study. Hence, there will be no control or comparison group, and therefore no need for randomization.

Visit 1 – Baseline/Screening Visit

The following screening activities will occur within 14 days of the study's original ablation procedure:

- The patient must be given ample time to review and sign the ICF.
- Collect demographic information (year and month of birth, sex, race, ethnicity).
- Review and collect medical, surgical, and radiation histories, including alcohol
 consumption and hepatitis, if applicable. Note: HCC diagnosis does not need to be
 reported as medical history.
- Review inclusion/exclusion criteria and determine if the patient is eligible for participation.
- Pain, using the Numeric Pain Rating Scale (NPRS).
- Quality of Life questionnaires: EORTC QLQ-C30 and liver-specific EORTC QLQ-

Confidential Page 36 of 61

HCC18.

- At minimum, an MRI of the liver must be taken at Baseline/Screening (per each study site's SOC) to ascertain tumor type, location, and size (measured in longest diameter and the diameter that is perpendicular to this longest diameter). The MRI must be taken within 14 days prior to ablation (Visit 2A). Ultrasound and/or CT are optional.
- Laboratory tests must be performed within 14 days prior to ablation (Visit 2A);
 otherwise the test(s) must be repeated.
 - Coagulation tests (PT, APTT, and INR).
 - Liver function tests (AST, ALT, GGT, albumin, indirect, direct and total bilirubin, and total protein).
 - o Renal function tests (Urea, creatinine, and electrolytes [sodium, potassium, and chloride]).
 - Complete blood count (differential cell count and platelet count).
 - o Alpha-fetoprotein test.
 - o Serum pregnancy test, for women of childbearing potential only.
- ECOG performance status.
- Child-Pugh score.
- ASA score.
- Include all relevant medications taken within 14 days prior to the ablation (Visit 2A).
 Relevant medications include chemotherapy, blood-thinning or coagulation, NSAIDs, those medications used to treat AEs, and those used for hepatitis (if concurrently treating).

Visit 2 - Ablation Through Discharge

The ablation procedure (Visit 2A), followed by post ablation observation and discharge (Visit 2B).

Visit 2A—Day of Ablation

Confirm inclusion and exclusion criteria prior to performing the activities below and collecting the respective data:

Ultrasound and/or CT scan to guide the probe to the tumor and confirm accurate
placement of the probe prior to emitting the microwaves. For ultrasound, a video of the
ablation may be submitted to the Sponsor. The ultrasound videos will be used to review
microbubble formation to see if there is a correlation with ablation area.

Confidential Page 37 of 61

06 AUGUST 2020, VERSION: 4.0

Procedure details:

- o Complete procedure time.
- Ablation time.
- Anatomical location of ablation.
- Number of probe placement attempts.
- Number of ablations.
- o Ablation maximum power and time used for each probe and ablation.
- Guidance method used.
- Number of ultrasound and/or CT scans performed for probe and margin assessment.
- Device accountability: type(s) and number of probes used.
- Any update to relevant concomitant medications. Exclude the elements of the medications that compose the anesthesia.
- All AEs and SAEs.

Visit 2B—Post ablation

The following data must be collected post ablation (up to 7 days after an ablation procedure):

- Pain, using the NPRS.
- Quality of Life questionnaires: EORTC QLQ-C30 and liver-specific EORTC QLQ-HCC18.
- MRI scans of the liver (within 7 days after completion of ablation procedure to confirm complete tumor ablation). The MRI scans will be reviewed for reconciliation with the data provided by the treating physician regarding the ablation.
- Laboratory tests.
 - Coagulation tests (PT, APTT, and INR);
 - Liver function tests (AST, ALT, GGT, albumin, indirect, direct and total bilirubin, and total protein).
 - Renal function tests (Urea, creatinine, and electrolytes [sodium, potassium, and chloride]).
 - o Complete blood count (differential cell count and platelet count).
 - Alpha-fetoprotein (AFP) test.
- ECOG performance evaluation.

Confidential Page 38 of 61

NeuWave Medical, Inc. NEU 2017 07

06 AUGUST 2020, VERSION: 4.0

- Length of hospital stay.
- Complete tumor ablation evaluation.
- Any update to relevant concomitant medications.
- Relevant concomitant procedures.
- All AEs and SAEs.

Post Ablation Follow-up Visits 3 to 11 (End of Study)

The following data will be collected post ablation at the post ablation follow-up visits, from Visit 3 through the end of the study (Visit 11), as follows:

- Pain score, using the NPRS (Visit 3 only).
- Quality of Life questionnaires: NPRS pain score, EORTC QLQ-C30 and liver-specific EORTC QLQ-HCC18.
- MRI of the liver.
- Laboratory tests.
 - Coagulation tests (PT, APTT, and INR).
 - Liver function tests (AST, ALT, GGT, albumin, indirect, direct and total bilirubin, and total protein).
 - o Renal function test (Urea, creatinine, and electrolytes [sodium, potassium, and chloride]).
 - Complete blood count (differential cell count and platelet count).
 - Alpha-fetoprotein (AFP) test.
- ECOG performance status.
- Complete tumor ablation evaluation (Visit 3 only)
- Local tumor progression (LTP) to be evaluated by a study physician based on MRI imaging. All MRI scans are to be submitted to the Sponsor.
- Progression-free survival to be evaluated by a study physician based on MRI imaging or may be reported by a patient's primary treating oncologist, if different than the study physician. If there is a progression, the study physician should specify if the progression is of the original target tumor, a new HCC tumor in the liver, or a distant metastasis.
- Any update to relevant concomitant medications.
- Relevant concomitant procedures.
- All AEs (if within 30 days post an ablation procedure).
- All SAEs through end of study.

Confidential Page 39 of 61 06 AUGUST 2020, VERSION: 4.0

Note: Repeat ablations may be performed on target tumor(s) only.

Unscheduled Visits

The following data will be collected at all unscheduled visits:

- Reason for the unscheduled visit.
- Relevant concomitant medications.
- Relevant concomitant procedures.
- AEs (if within 30 days post an ablation procedure) and all SAEs.

7.3. Monitoring Plan

This study will be monitored by the Sponsor to ensure:

- The rights and well-being of the patients are protected;
- Reported study data is accurate, complete, and verifiable from source documents; and
- The conduct of the study is in compliance with the currently approved protocol/amendment(s), applicable GCPs, and with applicable local regulatory requirements.

Steps to be taken to ensure the accuracy and reliability of data include the selection of qualified investigators and appropriate study centers, review of protocol procedures with the Investigator and associated personnel prior to the study, and periodic monitoring visits by the Sponsor. The Sponsor will review eCRFs for accuracy and completeness during on-site monitoring visits and after their return to the Sponsor; any discrepancies will be resolved with the Investigator or designees, as appropriate. The data will be entered into the clinical study database and verified for accuracy.

The extent and nature of monitoring will be predetermined and based on considerations such as the objective, design, complexity, and endpoints of the study and mutually agreed to by the Sponsor and investigators. Monitors will comply with established written standard operating procedures as well as procedures (i.e., monitoring plan) specified by the Sponsor for monitoring this study. These monitoring procedures are characterized in the monitoring plan for this study.

8. STATISTICAL CONSIDERATIONS

8.1. Statistical Design, Method and Analysis Procedure

This is a single-arm, prospective, multicenter study designed to evaluate the efficacy and safety of the NeuWave Certus Microwave Ablation System in the treatment of Chinese patients

Confidential Page 40 of 61

who have a single HCC tumor up to 5 cm or who have a maximum of 3 HCC tumors of up to 3 cm per tumor.

Categorical variables will be summarized descriptively by frequencies and associated percentages. Continuous variables will be summarized descriptively by number of patients, mean, standard deviation, median, minimum, and maximum. Confidence intervals will also be provided for procedure-related variables. A detailed Statistical Analysis Plan (SAP) describing all planned analyses of data collected in this study will be finalized prior to any analysis of data.

There will be three analysis populations defined for summary of data collected in this study. The primary analysis of safety and effectiveness endpoints will be performed on the Full Analysis Set, defined as all patients who are enrolled in the study, are not part of the run-in phase, and have the NeuWave Microwave Ablation System used for ablation. A Per Protocol analysis set will be defined as all patients in the Full Analysis Set who have no major protocol deviations. Effectiveness analyses will be repeated for the Per Protocol Set. The Safety Set will include all patients who provide informed consent and have MW ablation attempted with the NeuWave system and includes run-in phase patients. The Safety Set will be used for summarization of safety endpoints only. Safety and effectiveness data collected on patients participating in the run-in phase may be summarized separately from the remaining patients. There will be at least one planned subgroup analysis based on whether or not patients have a repeat ablation in the first 30 days to correct a margin (A1 to A0). A summary of all efficacy endpoints as well as adverse event summaries will be provided for all patients who only have the initial, planned ablation procedure at Visit 2A. These summaries will also be provided for all patients who receive a repeat ablation in the first 30 days.

The number and percentage of tumors achieving Technical Success will be summarized and a 95% confidence interval will be estimated. Technical Success will be evaluated based on the margin achieved after the first ablation and prior to any repeat ablations within the first 7 days.

A similar summary will be provided for Technical Efficacy. This endpoint will be based on the scan obtained at Visit 3 and will count as successes patients with A0 or A1 margins in that scan and who did not have an A2 margin since the Visit 2B scan. Additionally, if a patient received a repeat ablation for correcting a margin (to go from A1 to A0) within the first 30 days, this will also count as a success. Patients with repeat ablations to correct an A2 margin from Visit 2B to Visit 3 will not count as success for Technical Efficacy. The number and percentage of tumors with A0 and A1 margins will be presented as a subcategorization within each presentation of Technical Success and Technical Efficacy, as well as a summarization for the number and reasons for repeat ablations through Visit 3.

Local tumor progression rates at 1, 3, 6, 9, 12, 18, 24, 30, and 36 months will be estimated using the Kaplan-Meier method and 95% confidence intervals will be provided. Any repeat ablation required after Visit 3 (Month 1) will be identified as an instance of local tumor progression. A similar summary will be provided for the 36-month overall and progression-free survival rates.

Confidential Page 41 of 61

The number and percentage of patients experiencing AEs will be summarized at the preferred term level using the Society of Interventional Radiology (SIR) clinical practice guidelines for event categorization. A similar summary will also be provided for device-related AEs, procedure-related AEs, all SAEs, device-related SAEs, and procedure-related SAEs. Adverse event rates will also be estimated using cumulative patient years of exposure as the denominator as well as total number of patient ablations.

Three analyses of study data are planned. The first will occur after all enrolled patients have completed the 1-month visit and is intended to provide an initial estimate of device effectiveness for Technical Success as well as to summarize the peri-operative out to 1-month post-operative safety profile of patients undergoing MW ablation. A similar analysis will occur after all patients have completed the 12-month visit and will include a summary of local tumor progression rates as well as safety through one year. There are no plans to use the results of either analysis for the purpose of stopping the study early. The third analysis will occur after all patients have completed study participation.

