7.1.4. Measures to Reduce and Avoid Bias

There will be no central reviewer, however, all MRI scans and the ultrasound video taken on the day of ablation should be sent to the Sponsor.

The study related data will be recorded in the original Medical Records and reviewed during the monitoring process. Proper Training for the investigators will be planned to ensure all investigators have equal adequate experience with the device prior to commencing enrollment at their site. In addition, all sites will treat a minimum of 3 patients each, as part of the roll-in phase, which will only be included in the safety set. This is intended to reduce any operational bias due to learning curve.

The investigator should communicate further with the patients to improve the patient compliance. This will help to reduce the informational bias.

Confidential Page 27 of 61

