6.2 Full Analysis Set (FAS)

The Full Analysis Set (FAS) contains all subjects who are enrolled in the study, are not part of the run-in phase, and have the NeuWave Microwave Ablation System used for ablation. The FAS will be used for effectiveness endpoints and safety analysis.

Enrolled subjects means subjects who meet study entry criteria and sign the informed consent.

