6.4 Safety Analysis Set (SAF)

The Safety Analysis Set (SAF) contains all subjects who provide informed consent and have MW ablation attempted with the NeuWave system and includes run-in phase subjects. The Safety Set will be used for summarization of safety endpoints only.

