8.5 Safety Analyses

All outputs for safety outcomes will based on FAS and SAF.

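### The protocol makes the Full Analysis Set primary for safety, so run-in patients (12 of 137 planned) fall outside the primary AE and SAE rates; the Safety Set should lead instead.

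*Protocol*

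**What the plan says.** Protocol 8.1 gives the lead role for safety to the Full Analysis Set (FAS): "The primary analysis of safety and effectiveness endpoints will be performed on the Full Analysis Set". The same sentence limits the FAS to enrolled patients who "are not part of the run-in phase, and have the NeuWave Microwave Ablation System used for ablation".

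The paragraph then defines a Safety Set of consented patients who "have MW ablation attempted with the NeuWave system and includes run-in phase patients", and gives it one purpose: "The Safety Set will be used for summarization of safety endpoints only". It adds that run-in data may be summarised separately.

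The Synopsis and Protocol 7.1.4 both place run-in patients in the Safety Set only. Protocol 7.1.4 gives the reason for the run-in: "This is intended to reduce any operational bias due to learning curve".

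The SAP uses both sets and ranks neither:
- SAP 6.2: "The FAS will be used for effectiveness endpoints and safety analysis".
- SAP 6.4 defines the Safety Analysis Set (SAF) as consented subjects who "have MW ablation attempted with the NeuWave system and includes run-in phase subjects", and uses it for safety summaries.
- SAP 8.5: "All outputs for safety outcomes will based on FAS and SAF".
- SAP 8.5.1 plans an AE overview with run-in, FAS and total SAF counts.

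**The concern.** The run-in patients are fully treated with the study device and are the first cases at each site. Separating them from the effectiveness analysis has a stated reason, the learning curve. That reason does not carry over to safety, where early-use risk is part of what a complication rate should describe. Under Protocol 8.1 the one set that contains these patients is secondary for safety, which is the only purpose that set serves.

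The designation matters because little else in the plan says which figure to cite. The study is meant to support device registration in China (Protocol 4.3). There is no hypothesis and no acceptability criterion, and performance is to be judged in context with other available therapies (Protocol 8.4). In that setting the rate labelled primary is the natural one to set beside published rates. If the two sets differ, the plan as written supports leading with the one that omits the run-in cases.

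**Working it through.** **Step 1. Reproduce the plan's own sample size.** Inputs from Protocol 8.2.1 and SAP 7: 100 patients with data to at least 1 year, up to 20% dropout, 3 run-in patients at each of 4 sites.
- Main phase: 100 / (1 − 0.20) = 125.
- Run-in: 3 × 4 = 12.
- Total: 125 + 12 = 137, which matches.

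**Step 2. Share outside the primary safety set by design.** 12 / 137 = 8.8%. The denominator for primary safety is at most 125 on the FAS and at most 137 on the Safety Set. Twelve is the planned number; Protocol 7.1.4 speaks of a minimum of 3 per site, so it could be higher.

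**Step 3. Effect on the rate if run-in risk differs.** Assume an FAS rate of 3.8%, the major-complication rate cited in Protocol 10.2. This is illustrative and approximate: Protocol 4.1.1 gives the same percentage for 8 patients in a series of 221, and 8 / 221 = 3.6%. With a run-in rate of m × 3.8%, the Safety Set rate is (125 × 0.038 + 12 × m × 0.038) / 137.

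| m (assumed) | Expected events | Safety Set rate | Shift from 3.8% |
|---|---|---|---|
| 1 | 4.750 + 0.456 = 5.206 | 3.80% | 0.00 points |
| 2 | 4.750 + 0.912 = 5.662 | 4.13% | 0.33 points |
| 3 | 4.750 + 1.368 = 6.118 | 4.47% | 0.67 points |
| 4 | 4.750 + 1.824 = 6.574 | 4.80% | 1.00 point |

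**Step 4. The same in counts.** Suppose 5 events in the FAS: 5 / 125 = 4.0% (Clopper-Pearson 95% CI 1.3% to 9.1%).

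| Run-in events (assumed) | Safety Set |
|---|---|
| 0 | 5/137 = 3.6% |
| 1 | 6/137 = 4.4% |
| 2 | 7/137 = 5.1% |
| 3 | 8/137 = 5.8% |
| 4 | 9/137 = 6.6% |

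With no run-in events the Safety Set rate is the lower of the two. Two events would be 2 / 12 = 16.7% of the run-in, against 12 × 0.038 = 0.46 expected at 3.8%.

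**Step 5. Attempted but not completed ablations.** The documents give no number, so this is a deliberately extreme illustration. Take 5 events in the FAS, none in the run-in, and 1 to 3 abandoned main-phase attempts, each with a complication and each counted as outside the FAS. The FAS rate is 5/124 to 5/122 = 4.0% to 4.1%. The Safety Set rate is 6/137 to 8/137 = 4.4% to 5.8%.

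**The case against.** The strongest reply is that no exposed patient is missing from the planned safety results. The Safety Set has its own safety summaries in Protocol 8.1, SAP 8.5 bases every safety output on both sets, the AE overview shows run-in, FAS and SAF, and SAP 8.1.9 puts listings on the SAF unless otherwise specified. No hypothesis, threshold or stopping rule depends on the word primary, and Protocol 8.4 promises an evaluation of all the data. All of this stands. It limits the severity, but it gives no reason for the FAS to lead on safety.

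Three stronger readings are tempting, and the documents do not support them.

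- A reader might infer that run-in patients disappear from the complication figures. They are outside the primary analysis only. Neither document defines a headline complication rate; the safety endpoint in Protocol 7.1.2 is the rate of AEs and SAEs.
- A reader might infer that every abandoned ablation is excluded. That rests on a contrast between a device being used and an ablation being attempted, and neither document draws the line. A procedure stopped after energy delivery could count as use. Protocol 8.6, which restricts all analyses to patients undergoing ablation, adds to the uncertainty.
- A reader might infer that the FAS rate is biased in the device's favour. The documents give no run-in complication rate. Operators are already experienced in tumor ablation (Protocol 7.2.2), and training precedes enrolment (Protocol 7.1.4). At a 3.8% rate the chance of at least one event among 12 patients is 1 − 0.962^12 = 37%, but that holds for any 12 patients and shows no bias. If run-in patients do no worse than the others, the FAS rate is equal or higher.

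**Conclusion.** The point holds as a mis-assigned primary analysis set. Protocol 8.1 makes the FAS primary for safety, the run-in patients are outside it by definition (planned 12 of 137, 8.8%), and the SAP does not reverse the ranking. The learning-curve rationale explains their exclusion from effectiveness and does not extend to safety.

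The likely numerical effect is small and its direction is unknown. Under the assumed 3.8% FAS rate and a run-in rate one to four times as high, the primary rate would move by 0 to 1.0 percentage point, well inside the 1.3% to 9.1% interval around 5/125. The run-in multiples, the event counts and the abandoned-attempt scenario are all assumptions.

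Severity is moderate. The change is worth making because it is cheap and removes a selective exclusion from the primary AE and SAE rates, but no planned decision depends on it.

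**What to change.** - **Protocol 8.1:** take safety out of the sentence that makes the FAS primary, so that it covers effectiveness only. State that the Safety Set is the primary set for AE and SAE endpoints at all three analyses (1 month, 12 months, final).
- **SAP 6.2, 6.4 and 8.5:** state the same, with the FAS supportive for safety.
- **SAP 8.5.1:** keep the planned FAS and run-in columns as supportive summaries, so that any learning-curve difference stays visible.

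With the Safety Set leading, the undefined line between attempted and used no longer affects the primary safety rate. The restriction in Protocol 8.6 should be read or reworded to agree with that set.

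The cost is wording only: both sets of outputs are already planned and no new data are needed. Protocol 8.7 allows changes to planned analyses to be recorded in a protocol revision or an amended SAP. The downside is that the primary safety figure may turn out slightly less favourable.
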